9.1. Setting

This Medical Chart Review project will take place in Germany and especially in oncological and urological practices as well as in hospitals with urological/oncological departments and a high focus on systemic treatment for RCC.

It is planned to recruit up to n = 40 study sites with a distribution of 37.5% practices hematology-oncology, 37.5% practices urology and 25% hospitals with urological cancer focus. The number of study sites may increase if it becomes apparent that the number of patients to be recruited per site is lower than expected. The sites are addressed through direct contact by the project management of GermanOncology. As part of a feasibility process the potential case numbers and availability of study nurses or other documentation staff are also queried. All sites have to sign a service contract before start of study, in which rights and obligations as well as documentation fees are clearly defined.

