	
 ▪ Defined as median and rates of patients alive at pre-defined timepoints (12 and 18 months) after start of 1L therapy. ○ Proportion of different drug regimen in 1L 
 ▪ Defined as percentages of therapy protocols used as 1L therapy. ○ Best response rate (RR) in 1L 
 ▪ Defined as best response (complete response (CR) / partial response (PR) / stable disease (SD) / progressive disease (PD) / not done (ND)) recorded from the start of the therapy until disease progression/recurrence based on investigator's assessment. A confirmation of response is not required. ○ Duration of Response (DoR) in 1L 
 ▪ Defined as time from documentation of first disease response to disease progression. ○ Time to progression (TTP) in 1L 
 ▪ Defined as time from start of therapy until objective disease progression without including deaths. ○ Time to next treatment (TTNT) in 1L 
 ▪ Defined as time from last drug administered to initiation of next therapy. ○ Dose modifications and discontinuations in 1L 
 ▪ Defined of number of patients with at least 1 dose modification (reduction of dose or cancelling of administration) or with an interim/permanent discontinuation of one or all drugs of a therapy. ○ Handling after dose modification or discontinuations in 1L 
 ▪ Defined as continuation of therapies after dose modifications or temporary/permanent discontinuation of single drugs. 
The clinical outcomes will be analyzed for the total group of all patients and for following subgroups:
 
 ○ Age: < 70 years vs. ≥70 years ○ Gender: male vs. female ○ Risk rating: favorable (low) vs. intermediate vs poor (high) risk ○ Medical disciplines: urology vs. medical oncology ○ Institutions: practices vs. hospitals
Milestones	
Planned milestones:
 
 ● Start of data collection: 1 October 2022 ● Interim analysis (expected): 31 October 2022 ● End of data collection: 30 January 2023 ● Final study report: 15 April 2023

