8.2. Study Objectives

To answer these questions the following objectives are derived:

Primary Objective(s):

- Progression-free survival (PFS) for 1L therapies, expressed as median and as rates at timepoints of 6, 9, 12 and 18 months after start of 1L

Secondary Objectives:

- Overall survival (OS) of 1L therapies, expressed as median and rates at timepoints of 12 and 18 months after start of 1L therapy
- Best response in 1L overall and in dependence of administered drug regimen
- Progression-free survival of 1L therapies in dependence of specific drug regimen
- Pre- and post-treatments (i.e. surgery, radiotherapy, medicinal therapies) before/after TKI + ICI and ICI + ICI in 1L
- Duration of response (DoR) in 1L overall and in dependence of administered drug regimen (TKI + ICI or ICI + ICI)
- Frequency of dose modifications and temporary/permanent discontinuations of 1L therapies and their reasons
- Proportions of modifications by dose reduction compared to cancelling single applications
- Effectiveness (PFS, OS and best response) of administered 1L therapies under real world conditions by medical specialty (urology, medical oncology) and setting (practice, hospital)

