9.2. Variables

The following variables will be captured by a specific eCRF and are needed for the analysis of all outcomes and for answering all research questions.

Tab. 2: List of all variables, role, data source and operational definitions

Variable	Role	Data source(s)	Operational definition
Age and gender	baseline characteristic	Medical Chart	Years; male/female
Weight and body surface	baseline characteristic	Medical Chart	kg, m ²
Date of first diagnosis	baseline tumor characteristic	Medical Chart	dd/mm/yyyy
Stage and risk rating (IMDC) at first diagnosis and at start of 1L	baseline tumor characteristic	Medical Chart	Favorable risk / intermediate risk / poor risk
Assessments and results of PD-L1 expression as TPS	baseline tumor characteristic	Medical Chart	y/n; 0-100%
Non-medicinal pre-treatments (primary OP, cytoreductive nephrectomy radiotherapy)	baseline tumor characteristic	Medical Chart	y/n; dd/mm/yyyy of OP; mode of OP; intention of OP (curative/palliative); period and dose of radiotherapy
Medicinal pre-treatments (adjuvant, neoadjuvant)	baseline tumor characteristic	Medical Chart	y/n; start/stop and used therapy protocol
Location of administration and performing medical discipline	Relevant for outcomes	Medical Chart	Urological practice; hematological practice; hospital with urological department; hospital with oncological department
Administered drugs / protocols in 1L	Relevant for outcomes	Medical Chart	administered therapy protocol
If applicable: Reason for ineligibility of ICI	Relevant for outcomes	Medical Chart	Concomitant disease; patient's wish
Duration of 1L	Relevant for outcomes	Medical Chart	Start/stop of therapy or every cycle;

Dates of administrations for i.v. drugs in 1L	Relevant for outcomes	Medical Chart	Dates of every administration
Dosages per administration	Relevant for outcomes	Medical Chart	Dose of administered drugs per administration
Dose modifications or drug administration cancelling or interim/permanent discontinuations of single drugs / complete therapy in 1L	Relevant for outcomes	Medical Chart	Each for single/all drugs: Dose modification; cancelling single administration; temporare discontinuation; permanent discontinuation
Reasons for modifications, cancelling of single administrations and discontinuations in 1L	Relevant for outcomes	Medical Chart	Each for single/all drugs: intolerance; age; performance status; patient's decision; other

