- Number of urological practices: 15
- Number of oncological practices: 15
- Number of hospitals with urological focus: 10
- Total number of sites across Germany: 40

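### The one-way urology–oncology and practice–hospital splits risk partly mixing specialty with setting, because the site plan secures no oncology-department hospital patients

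*Combined protocol and SAP*

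**What the plan says.** **Sites.** Section 9.1 gives the planned mix as "37.5% practices hematology-oncology, 37.5% practices urology and 25% hospitals with urological cancer focus", and section 9.4 repeats it as a count: "Number of hospitals with urological focus: 10", next to 15 urological and 15 oncological practices. The only patient yield assumed for hospitals, also in section 9.4, is for urologically focused ones. The sentence in section 9.1 just before the site mix is wider and speaks of "hospitals with urological/oncological departments and a high focus on systemic treatment for RCC".

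**Data.** Table 2 (section 9.2) records the place of treatment in four categories: "Urological practice; hematological practice; hospital with urological department; hospital with oncological department".

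**Analysis.** The Abstract (Data Analysis) lists the subgroups one by one, among them "Medical disciplines: urology vs. medical oncology" and "Institutions: practices vs. hospitals". Neither there nor in section 9.6 is a cross-classification, stratification or adjustment named. Section 9.6 leaves detailed methods to a separate statistical analysis plan.

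**Purpose.** Section 8.2 makes PFS, OS and best response by specialty and by setting a secondary objective. Section 8.1 asks whether disciplines differ in how they handle modifications. Section 7 singles out both comparisons as a reason for the study.

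**Enrolment.** Section 9.1.2 makes enrolment competitive with no cap per site. The only quotas are by regimen, in Part 2.

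**The concern.** If hospital patients fall mainly on the urology side, the urology group mixes practice and hospital patients while the oncology group consists mainly of practice patients. Patients reaching hospitals and practices may differ in prognosis and management. A crude specialty difference would then contain part of the setting difference, and a crude practice–hospital difference would contain part of any specialty difference. A reader could take a gap in PFS, or in the handling of modifications, as a difference between urologists and oncologists when some of it reflects where patients were treated. Section 9.8 does not warn of this.

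**Working it through.** **The plan's own figures**

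- Sites: 40 × 0.375 = 15, 40 × 0.375 = 15 and 40 × 0.25 = 10. These agree with section 9.4.
- Sample size (section 9.4; z = 1.96, π = 0.5, E = 0.05, N = 10,000): 0.9604 × 10,000 / (0.9604 + 0.0025 × 9,999) = 9,604 / 25.958 = 369.98, rounded up to 370. The plan then sets 400.

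**Inputs**

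- From section 9.4: n = 400; practice-to-hospital split 65:35; urology-to-oncology split within practices 50:50.
- Assumed: f, the share of hospital patients treated by oncology departments, varied from 0 to 0.50; and a true hospital–practice difference of 10 points in a PFS rate, with no specialty effect.

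**Patient numbers**

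Practices: 0.65 × 400 = 260, so 130 urology and 130 oncology. Hospitals: 0.35 × 400 = 140, of which 140(1 − f) are urology and 140f oncology.

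**Shift in the crude specialty difference**

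Shift = 10 × [140(1 − f) / (130 + 140(1 − f)) − 140f / (130 + 140f)].

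| f | Hospital share, urology | Hospital share, oncology | Shift (points) |
|---|---|---|---|
| 0 | 140/270 = 51.9% | 0/130 = 0% | 5.2 |
| 0.10 | 126/256 = 49.2% | 14/144 = 9.7% | 3.9 |
| 0.25 | 105/235 = 44.7% | 35/165 = 21.2% | 2.3 |
| 0.50 | 70/200 = 35% | 70/200 = 35% | 0 |

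Above f = 0.50 the sign reverses.

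**Mirror case**

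Practices are half urology and hospitals are a share (1 − f) urology. An assumed 10-point specialty effect with no setting effect would therefore shift the crude setting difference by 10 × [(1 − f) − 0.5]: 5.0, 4.0, 2.5 and 0 points at the same four values of f.

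**Sensitivity to the patient mix**

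The site yields in section 9.4 give 15 × 8–12 = 120–180 patients in each practice type and 10 × 16–24 = 160–240 hospital patients. That is 400–600 in total at 60:40, not the stated 65:35. At f = 0 the hospital share of urology would be 160/280 = 57% and the shift 5.7 points.

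**Precision**

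95% half-width at p = 0.5, simple binomial, ignoring censoring and clustering by site:

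- Crude specialty contrast at f = 0: 1.96 × √(0.25/270 + 0.25/130) = 10.5 points.
- Specialty within practices: 1.96 × √(0.25/130 + 0.25/130) = 12.2 points.
- Crude setting contrast: 1.96 × √(0.25/260 + 0.25/140) = 10.3 points.
- Setting within urology at f = 0: 1.96 × √(0.25/130 + 0.25/140) = 11.9 points.
- Specialty within hospitals at f = 0.10: 1.96 × √(0.25/126 + 0.25/14) = 27.6 points.

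**The case against.** A urological cancer focus describes the hospital, and renal cell carcinoma is a urological cancer; the phrase does not say which department treats the patient. Section 9.1 mentions oncological departments and Table 2 has a category for them. The background also refers to urologists and hematologists in both practices and hospitals. All of this stands. A reader might infer that the oncology group contains no hospital patients by design, but the document does not say so: 0% is the extreme case f = 0.

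A reader might also infer that specialty and setting cannot be separated at all. That does not follow either. With 15 urological and 15 oncological practices, specialty can be compared within practices whatever f is, and the variable needed is already collected. Nor is 5.7 points the plan's figure: it comes from the site yields, whereas the stated split gives 5.2, and uncapped competitive enrolment means that site counts do not fix the patient mix.

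Finally, the Abstract gives a list of subgroup variables that does not rule out cross-classification, and the separate statistical analysis plan may add it. The comparison is secondary and descriptive. These points limit the weight of the concern. They do not remove it, because the protocol as written names only the one-way splits and secures no oncology-department hospital patients.

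**Conclusion.** The concern holds as a risk of partial confounding of unknown size. The range is about 5.2 points (f = 0) to none (f = 0.50) in the crude specialty difference for each assumed 10-point setting difference, with a similar effect in the other direction. It rests on n = 400, the stated 65:35 and 50:50 splits, and the assumed 10-point effect; f is not documented. The bias cancels only if hospital patients divide about equally between the two specialties, and nothing in the site plan aims at that. The matter is worth settling before analysis because these comparisons are stated questions and the remedy is cheap.

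**What to change.** 1. Report the specialty and setting outcomes by the four-category location variable in Table 2, with the number of patients in each cell.
2. Make the specialty contrast within practices, or stratified by setting so that any oncology-department hospital patients are kept. Make the setting contrast within specialty, or stratified by it.
3. Reconcile the urological focus in the site plan with the urological/oncological departments in section 9.1 and with Table 2, and state how a hospital patient is assigned to a specialty.
4. Add to section 9.8 that the two factors can be separated only to a limited extent if few oncology-department hospital patients are enrolled.

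**Cost.** This changes wording and tables only; no new data are needed. The within-practice specialty contrast is less precise and speaks to office practice only, leaving out the 35% of patients treated in hospitals. Stratifying keeps those patients in the analysis but gains little when the oncology-hospital cell is small: at f = 0 the hospital stratum adds nothing, and at f = 0.10 it holds only 14 oncology patients.

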9.1.1. Inclusion criteria

Patients must meet all of the following inclusion criteria to be eligible for inclusion in the study:

Part 1 and 2:

- Patients aged ≥ 18 years old
- Patients with histologically/cytologically confirmed renal cell carcinoma (ICD-10 C64)
- Full medical information regarding all treatments before, during and after 1L should be available.

Specific inclusion criteria only for Part 1:

- Patients with locally advanced or metastatic disease and a start of any systemic 1L therapy against RCC between 01 January 2020 and 31 December 2021

Specific inclusion criteria only for Part 2:

- Patients with locally advanced or metastatic disease, who were treated with a combination of ICI + TKI or ICI + ICI as 1L therapy against RCC and who had a completion of this therapy between 01 January 2020 - 31 December 2021 with a follow-up period of at least 3 months after completion of the 1L.

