9.1.2. Exclusion criteria

Exclusion criteria for part 1 and 2

Patients meeting the following criteria will not be included in the study:

- Patients participating in an interventional clinical study within 30 days before start of 1L

All sites are asked to document all of their patients with the fulfilled inclusion and not fulfilled exclusion criteria, starting with the earliest start (in part 1) and the longest follow-up period (in part 2), respectively. The patients should be treated with the systemic 1L therapy in the site and data should be available in the medical records of the sites. The enrollment will be competitively over all participating sites without a limitation for the single sites. In part 2 quotas for groups with ICI + TKI and ICI + ICI and with the specific therapy avelumab + axitinib or nivolumab + ipilimumab will be set up.

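### In Part 1, requiring full information on treatment after 1L makes entry depend on post-index events linked to PFS; the criterion should stop at the end of 1L

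*Combined protocol and SAP*

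**What the plan says.** Section 9.1.1 opens with "Patients must meet all of the following inclusion criteria to be eligible for inclusion in the study". One criterion for both parts, repeated in the abstract under Population, is "Full medical information regarding all treatments before, during and after 1L should be available".

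Section 9.1.2 asks sites to document all patients who fulfil the criteria and adds: "The patients should be treated with the systemic 1L therapy in the site and data should be available in the medical records of the sites". Section 9.6 restricts the analysis to evaluable patients who meet the inclusion criteria.

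The two parts enter patients differently. Part 1 needs "a start of any systemic 1L therapy against RCC between 01 January 2020 and 31 December 2021"; 1L need not have ended. Part 2 takes combination-therapy patients "who had a completion of this therapy between 01 January 2020 - 31 December 2021". It also asks for no less than three months of observation once 1L has ended.

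Other text is more permissive. Section 9.5 lets the eCRF record run to the present, to death or to loss to follow-up. Section 9.8 says unavailable data are to be documented as unavailable, but also allows a patient with much missing data to be rejected.

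The primary objective is median PFS and PFS rates at 6, 9, 12 and 18 months. A secondary objective (Section 8.2), which covers both specialty and setting, begins "Effectiveness (PFS, OS and best response) of administered 1L therapies under real world conditions by medical".

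**The concern.** Whether a patient can be entered should be settled by what is known at the start of 1L. Here it also depends on what happens afterwards, and the condition falls unevenly. Take two Part 1 patients who start on the same day. One is still on 1L at chart review, has no later treatment, and cannot fail the after-1L element. The other progressed and received second-line therapy elsewhere; if that therapy is not in the site's chart, a literal reading makes this patient ineligible. Table 2 lists progression among the reasons for the end of 1L, so the patients at risk of exclusion are enriched for PFS events.

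The primary endpoint would then be estimated in a sample that has lost some of its failures. A larger sample would not help, and no analysis plan can recover patients who were never entered. The documents ask for no count of patients left out under this rule, so the loss could not be measured later. Time to next therapy and the description of subsequent therapies would be selected in the same way.

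**Working it through.** **1. Reading the sections together.** The criterion sits on a must-meet list (9.1.1), sites document only patients who fulfil it (9.1.2), and the analysis set repeats the condition (9.6). Sections 9.5 and 9.8 describe records already entered. They conflict with the entry rule but do not switch it off.

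**2. The plan's own precision target (9.4).** With z = 1.96, π = 0.5, E = 0.05 and N = 10,000:

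n = 0.9604 × 10,000 / (0.9604 + 0.0025 × 9,999) = 369.98, rounded up to 370.

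This reproduces. The yardstick for PFS rates is therefore a margin of 5 points.

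**3. Inputs for the size of the effect.**
- Median PFS m: 8.4 to 15.1 months (abstract, Study Size; Section 9.4 prints the upper value as 151).
- Follow-up: 1L starts run over 24 months and data collection from 1 October 2022 to 30 January 2023. Latest starters thus have 9 to 13 months and earliest starters 33 to 37. The calculation uses 12 to 36 months, uniform.
- Share q of patients with an observed PFS event who are excluded: **assumed** 10%, 20% or 30%; the documents give no transfer figure.
- **Assumed** as well: exponential PFS, exclusion unrelated to the time of progression, and a PFS event standing in for the end of 1L.

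**4. Formula for 12-month PFS.** Everyone has at least 12 months of follow-up, so the estimate is a simple proportion among retained patients. Let S = 2^(−12/m), and let s be the share event-free at cut-off, s = (2^(−12/m) − 2^(−36/m)) × m / (24 ln 2). Then

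estimate = [(1 − q)S + qs] / [(1 − q) + qs].

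- m = 8.4: S = 0.3715, s = 0.1617. For q = 30%: (0.2601 + 0.0485) / (0.7 + 0.0485) = 0.412.
- m = 15.1: S = 0.5765, s = 0.3494. For q = 30%: (0.4035 + 0.1048) / (0.7 + 0.1048) = 0.632.

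| q | 12-month PFS, m = 8.4 (true 37.1%) | 12-month PFS, m = 15.1 (true 57.6%) |
|---|---|---|
| 10% | 38.3% (+1.1) | 59.2% (+1.6) |
| 20% | 39.6% (+2.4) | 61.0% (+3.4) |
| 30% | 41.2% (+4.1) | 63.2% (+5.5) |

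Differences are taken before rounding. Simulation with follow-up of 9 to 33 or 13 to 37 months gives +0.9 to +1.7 points at q = 10% and +3.7 to +6.1 at q = 30%. In those runs the 18-month shift at q = 30% is +4.3 to +7.7 points, and the median becomes 9.2 to 9.5 months instead of 8.4, or 18.4 to 18.9 instead of 15.1.

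**5. What makes it smaller.**
- Deaths on 1L cannot fail the after-1L element. If 15% of events are such deaths (assumed), the effective q is 0.85 × 30% = 25.5%, and the 12-month shift falls to +3.3 (m = 8.4) or +4.5 (m = 15.1).
- Table 2 also lists intolerance, physician decision and patient's wish as reasons for ending 1L. Such patients can be excluded without having progressed. Simulating a 12-month median with 15% deaths and 20% of 1L ends not due to progression (both assumed), 30% removal gives 53.0%. Without these two dilutions it gives 55.2%; the true value is 50.0%.

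**6. What reverses it.** Suppose only patients progressing after month 9 leave, with q = 30%. The removed share is 0.3 × (S(9) − s), which is 0.3 × 0.3142 = 0.0943 for m = 8.4 and 0.3 × 0.3122 = 0.0937 for m = 15.1. Six-month PFS becomes (0.6095 − 0.0943) / 0.9057 = 0.569 (−4.1 points) or (0.7592 − 0.0937) / 0.9063 = 0.734 (−2.5). Twelve-month PFS becomes (0.3715 − 0.3 × 0.2098) / 0.9057 = 0.341 (−3.1) or (0.5765 − 0.3 × 0.2271) / 0.9063 = 0.561 (−1.6).

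**7. Part 2.** Every patient has completed 1L, so there is no still-on-1L group. Removal at random thins the sample without changing the PFS distribution: simulated medians stay at about 8.1 and 12.7 months for q = 0, 20% and 40%.

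**The case against.** The strongest reply is that exclusion is inferred. The criterion itself names no location for the data. The sentence that does, in 9.1.2, concerns patients treated with 1L at the site and does not mention later therapy. Both say should. Loss to follow-up and documented missing data are foreseen in 9.5 and 9.8. Table 2 takes surgery, radiotherapy and adjuvant treatment from the same charts, which suggests that charts are expected to hold some treatment given elsewhere. All of this stands against the stronger reading a reader might draw, that patients who moved are certainly excluded. It does not remove the problem. The line is on a must-meet list, 9.6 carries it into the analysis set, and 9.5 and 9.8 apply after entry. About 40 sites would have to settle the conflict themselves, and rejected records are unpaid (9.3), which favours the strict reading.

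Three further inferences are not supported:
- That bias is upward in both parts. Part 2 lacks the contrast, and in Part 1 the direction depends on who leaves.
- That the bias uses up the whole 5-point margin. That needs q of roughly 20% to 40%, depending on the median and time point, before dilution.
- That a specific false difference arises between specialties or settings. Unequal hand-over would produce one, but the documents give no rates.

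Section 9.6 defers methods to a separate SAP. A SAP could set the censoring rule but could not repair eligibility.

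**Conclusion.** The point holds for Part 1 as a conditional risk. Eligibility depends on information that arises after the start of 1L, and patients still on 1L, or who died on it, cannot fail that element. Applied literally, the rule would probably raise 1L PFS: by about 1 to 6 points at 12 months if 10% to 30% of patients with events are removed, with medians of 8.4 to 15.1 months and follow-up of 12 to 36 months. Deaths on 1L and other reasons for ending it reduce this; departure mainly of late progressors can reverse it. The removed share is an assumption throughout, so the size is illustrative. The conflict between 9.1.1 and 9.1.2 on one side and 9.5 and 9.8 on the other is in the text and must be reconciled whatever that share is. For Part 2 no PFS bias of this kind was found under random removal.

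**What to change.** Before data collection starts:

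1. In the abstract and in 9.1.1, limit the criterion to information before and during 1L. Limit the availability sentence in 9.1.2 in the same way, and align 9.5 and 9.8 with it.
2. Keep patients who leave the site after 1L. Count progression or death when documented; otherwise censor at the last tumour assessment at the site.
3. Record later therapy with a value for not available / treated elsewhere. Treat it as missing for time to next therapy and subsequent therapies only.
4. Add a sensitivity analysis that counts hand-over without documented progression as a PFS event, because hand-over may coincide with progression and the censoring in step 2 may then be informative.
5. Have each site report the number of patients excluded, with reasons.

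The cost is a change of eligibility wording, one drop-down value, a short count per site and one extra analysis. The downside is some missing post-1L data and possibly informative censoring; both should be reported. Once sites have screened under the current wording, analysis cannot recover the patients left out.
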